4.4 Removal of Subjects from Study

Subjects can be taken off the study treatment and/or study at any time at their own request or if deemed necessary by the study team due to distress.

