1.2 Study Agent(s)/Therapy(ies) Background and Associated Known Toxicities

The mYPAS observational scale will be used to assess VR and non-VR distraction for decreasing preoperative/procedural anxiety in pediatric oncology patients undergoing port access. It is an observational scale that consists of five domains (activity, emotional expressivity, state of arousal, vocalization and use of parents) and has shown good to excellent inter-observer reliability (2). It can be applied to children two years and older although it was validated for use in the 5-12 age group (2).

VR technology can be used as a distractor to decrease preoperative/procedural anxiety in pediatric oncology patients undergoing port access. Side effects of VR technology are minimal but include motion sickness and nausea.

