4.2 Procedures During Treatment

Once it is confirmed that the subject qualifies and the parents (LARs) are willing to participate, the parents (LARs) will be given the demographics form to fill out and the subject will be randomized in the study system. Whether the patient participates in the Virtual Reality group or the Non-Virtual Reality group first will depend on a computerized randomization process independent of the study researchers.

For the Non-virtual reality group, a member of the study team will evaluate the patient using the mYPAS prior to port access. Parents will be asked to fill out a questionnaire evaluating their child's preoperative anxiety after port access is complete (see study schema).

For the port access with virtual reality (VR) distraction, the patient will be able to play the VR game for 15 minutes prior to actual port access procedure start. During this first 5-15 minutes of being in their CCBD procedure/infusion room with the placement of the VR headset, a researcher will be doing the first mYPAS observation and scoring (Holding). The patient will then continue to play the game through the port access procedure. The point where the port access kit is opened by the nurse marks the start of the Port access portion of the mYPAS observation (Induction 1). The end of the second mYPAS observation is when the Tegaderm dressing is applied to the port access needle.

After port access is complete with VR, or control, the parents or LAR will then be asked to fill out a questionnaire assessing their child's perioperative anxiety.

NOTE: For safety of the researchers and patients, all mYPAS patient observations on day of CCBD visit, as well as any further consent questions, will be performed through a virtual telemedicine platform with approved tablets run and vetted by telemedicine at Children's Health System of Texas (CHST). The process has already been approved and vetted by CHST telemedicine so that there is little to no risk of virtual PHI breach. The observation of the patients will be done in real time with no recording of the encounter. Tablets are currently in place from CHST, and nursing and Child Life are informed of process.

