5.0 SAFETY MONITORING

5.1 Definition of an Adverse Event

Any issues experienced while being observed by the research team should be recorded as a potential adverse event for evaluation by the PI as to the seriousness, relatedness, and expectedness in relation to the study.

It is expected that a patient may experience some discomfort or motion sickness while using VR.

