5.2 Data and Safety Monitoring Plan

The researchers will be monitoring should a patient encounter any issues, particularly any discomfort or motion sickness while using the VR device. If so, the VR device will be removed, and the subject will be eliminated from the study.

The study staff will record all concerns experienced by enrolled subjects, the total number of side effects experienced by all enrolled subjects, and the number of subjects eliminated from the study due to side effects.

Reporting requirement: The principal investigator will oversee the subject safety and data records and report all pertinent information to the IRB, as necessary.

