7.2 Sample Size and Accrual

To fully power our study, we will recruit 77 patients to detect a difference of 3.5 in the mYPAS score; assuming a standard deviation of 10, a 10% reduction in patient participation due to attrition, and a power of 0.8. If attrition exceeds 10% additional post hoc power analysis will be performed.

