8.4 Data Management and Monitoring/Auditing

Only the subjects assigned unique study number will be used on study questionnaires, staff mYPAS assessments, and exclusion log. The only link to participants identity will be the electronic subject enrollment log, which will include only the name, date of port access appointments, medical record number, and unique study ID #.

A password-protected computer file will be created, and all study data will be saved on a Children's Medical Center computer, in the secure research file, kept behind the Children's Health firewalled system. The secure research file will be limited access, only members of the study team will be given password access for the purpose of data analysis.

At the conclusion of study enrollment, the data from the questionnaires and assessment forms will be transferred into the secure study REDCap database, and the paper forms will be properly discarded according to HIPPA standards at Children's Health System. In addition, the electronic enrollment and exclusion log will also be properly discarded. No paper documents or link to study participants identities will be retained.

REDCap is the UTSW SCCC institutional choice for the electronic data capture of case report forms for SCCC Investigator Initiated Trials. REDCap will be used for electronic case report forms in accordance with Simmons Comprehensive Cancer Center requirements, as appropriate for the project. All the study data will be stored within the UTSW RedCap system, which is stored behind the secure UTSW firewall.

The UTSW Simmons Comprehensive Cancer Center (SCCC) Data Safety Monitoring Committee (DSMC) is responsible for monitoring data quality and patient safety for all UTSW SCCC clinical trials. As part of that responsibility, the DSMC reviews all local serious adverse events and UPIRSOs in real time as they are reported and reviews adverse events on a quarterly basis. The quality assurance activity for the Clinical Research Office provides for periodic auditing of clinical research documents to ensure data integrity and regulatory compliance. A copy of the DSMC plan is available upon request.

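### Removal for distress (4.4) and VR-only elimination (5.2, 6.1) can take children out because of their outcome; if their scores or second visits are lost, the estimate is biased in a direction set by which visits are stopped

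*Combined protocol and SAP*

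**What the plan says.** Section 4.4 allows removal at the child's own request or "if deemed necessary by the study team due to distress". It covers coming off treatment, off study, or both. It does not define distress or say which form of removal applies.

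Section 1.2 describes the mYPAS as an observer scale with "five domains (activity, emotional expressivity, state of arousal, vocalization and use of parents"). Section 4.2 has it scored live over a tablet, without recording. At a VR visit, "a researcher will be doing the first mYPAS observation and scoring (Holding") during play before the procedure; a second observation runs from the opening of the access kit to the dressing. For non-VR visits 4.2 describes scoring before port access, while the objective in the Study Summary covers both before and during.

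Section 5.2, repeated in substance in 6.1, says that on discomfort or motion sickness "the VR device will be removed, and the subject will be eliminated from the study". Non-VR visits have no matching rule.

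On records, 5.1 says "Any issues experienced while being observed by the research team should be recorded" as potential adverse events, 5.2 has staff count "the number of subjects eliminated from the study due to side effects", and the monitoring committee in 8.4 "reviews adverse events on a quarterly basis". On losses, 7.2 says "If attrition exceeds 10% additional post hoc power analysis will be performed". Section 7.3 names a paired test and a mixed model, with no rule for missing scores. Section 4.3 plans a second visit for each subject but does not mention children who were stopped. The study schema and datasheet contents are not in the text available, so nothing is inferred from their absence.

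**The concern.** The trigger for removal overlaps with the primary outcome. A child who is visibly upset, aroused and vocal at port access scores high on the mYPAS and is also the child most likely to be judged distressed. If that child leaves the study and the visit goes unscored, the data are missing because of their own value. A paired test then drops the pair. A likelihood-based mixed model is no remedy, because it relies on the missingness being explained by observed scores, and here the decisive score was never written down.

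The direction depends on where stops occur. The one route that the plan makes mandatory, 5.2 and 6.1, exists only at VR visits, so an imbalance towards VR stops is plausible. If those children have high scores, VR would look better than it is. The safeguard in 7.2 looks only at the number lost and responds with a power calculation, which would not reveal this.

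**Working it through.** **Inputs from the plan.** Difference 3.5, SD 10, 77 children, 10% attrition, power 0.80 (7.2). Two-sided alpha 0.05, final boundary ±2.004, negative Z favouring VR (7.4).

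**Assumed.** Normal scores with between-visit correlation 0.5, so the SD of the difference is √(2 × 10² × (1 − 0.5)) = 10. Removal applies to 25%, 50% or 100% of children above the non-VR 90th percentile, and removed pairs are lost. The plan gives no removal rate.

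**1. The plan's own figure.** A paired t-test with SD of differences 10 needs 67 pairs; 67/0.9 = 74.4, so 75, close to the stated 77. Then 77 × 0.9 = 69.3, so 69 pairs. At the final boundary alone, power is Φ(3.5/(10/√69) − 2.004) = Φ(0.903) = 0.82, and false efficacy is Φ(−2.004) = 0.023.

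**2. Stops at VR visits only, no true effect, half of those above the cut-off removed.**
- Mean excess in the top tenth: 10 × φ(1.2816)/0.10 = 17.55. The within-child difference carries (1 − 0.5) of it: 8.775.
- Pairs lost: 0.5 × 10% = 5%, which alone is below the 10% trigger in 7.2.
- Retained mean difference: −0.05 × 8.775/0.95 = −0.46.
- Retained variance of the VR score: second moment above the cut-off is 100 × (1 + 1.2816 × 1.755) = 324.9; (100 − 0.05 × 324.9)/0.95 − 0.924² = 87.3. SD of differences: √(0.25 × 87.3 + 75) = 9.84.
- Shift in Z with 69 pairs: −0.46/(9.84/√69) = −0.39.
- False efficacy: Φ(−2.004 + 0.39) = 0.053.

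Across correlations 0.3 to 0.7, with the SD of differences held at 10, this is 0.045 to 0.062.

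**3. All patterns, complete pairs, at 25% / 50% / 100% removal.** With a 3.5 benefit and VR-only stops, the cut-off lies 1.2816 + 0.35 = 1.63 SD above the VR mean. The share above is 5.14% and the mean excess 20.51, so at 100% the shift is 0.0514 × 10.26/0.9486 = 0.56. The same-rule rows come from simulating 4,000,000 pairs.

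| Stops | True effect | Estimated benefit | Consequence at ±2.004 |
|---|---|---|---|
| Same rule at both visits | none | 0 | no bias |
| Same rule at both visits | 3.5 benefit | 3.40 / 3.29 / 3.05 | power 0.81 / 0.79 / 0.75 |
| VR visits only | none | 0.22 / 0.46 / 0.97 | false efficacy 0.035 / 0.053 / 0.12 |
| VR visits only | 3.5 benefit | 3.63 / 3.77 / 4.06 | benefit overstated |
| Non-VR visits only | 3.5 benefit | 3.28 / 3.04 / 2.53 | power 0.77 / 0.71 / 0.57 |

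**4. Mixed model.** One million simulated children, maximum likelihood with treatment, period and sequence, standard errors scaled to 77; VR-only stops, no effect, a first-visit stop cancelling the second visit. The estimates are −0.29 / −0.58 / −1.25 and false efficacy is 0.040 / 0.067 / 0.18. A separate factored-likelihood calculation with 10% of children removed gives −1.27. If the full score of the stopped visit is kept, the estimate is 0.0 and false efficacy 0.02.

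**5. Why the second visit matters too.** Take 10% of children removed, a true benefit of 3.5, correlation 0.3 to 0.7, the stopped score kept but no second visit after a first-visit stop. The complete-pairs estimate is still biased by −0.36 to −0.54 (VR-only stops) or +0.35 to +0.55 (non-VR-only stops). The likelihood model's bias is at most 0.01.

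**The case against.** Section 4.4 is a routine, permissive safety clause. It does not say that scores are discarded, and its wording allows a child to stop the session and stay on study. Section 4.3 plans a second visit for each subject, and unseen forms may settle the matter. All of this stands: the loss of scores is a condition of the argument, not a finding.

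Timing also weakens the premise. A VR child who becomes upset at access already has a Holding score, and on the text of 4.2 a non-VR child may have been scored before access. A non-VR visit offers little to stop, so stops there are less likely than at VR visits. That too stands in part, although no section says that the earlier score would be used.

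Four stronger readings are tempting and unsupported:
- *The VR-only rule inflates the VR benefit.* Discomfort and motion sickness are not anxiety, and nothing shows that these children score high on the mYPAS.
- *False efficacy of 0.12 or 0.18.* These need every child above the cut-off to be removed at VR visits and nobody at non-VR visits. In step 3 that is 10% of pairs, the plan's whole attrition allowance.
- *The harm boundary in 7.4 is disabled.* With a uniform harm of 3.5 and half of those above the non-VR 95th percentile removed, the chance of crossing +2.004 falls from 0.82 to 0.79 (both visits) or 0.72 (VR only). The steep fall, 0.59 to 0.34 or 0.27, needs the harm concentrated in 15% of children, about 3.5/0.15 = 23 points each; with 10% removal it is 0.55 or 0.53. These figures are for the final boundary only, not the interim ±2.431, and adverse-event review is a separate route.
- *The direction could never be known afterwards.* The records under 5.2, with the known sequence, may allow stops to be assigned to a condition. The plan simply does not ask for it.

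**Conclusion.** The concern holds in conditional form and merits a modest amendment. Following 4.4, 5.2 and 6.1 as written can remove children because of their outcome, and no visible section protects their scores or second visits. If those are lost, neither analysis in 7.3 corrects it. The directions are general given that stopped visits are high-scoring ones: towards zero for a true effect under a common rule (none under no effect), in favour of VR if stops are mainly at VR visits, against VR if mainly at non-VR visits.

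The size is unknown. The rise from 0.023 to about 0.05 assumes correlation 0.5, half of the top tenth of VR-visit scores removed, and total loss of those pairs. With few stops, or scores kept in practice, the effect is small or nil. It is not a demonstrated bias.

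**What to change.** - **4.4, 5.2 and 6.1:** distress, or discomfort with the headset, ends the VR or distraction session but not study participation, unless the child or family withdraws or the team judges a further visit unsafe. The clinical decision to stop is unchanged.
- **Scoring:** port access goes ahead as standard care, so continue the live mYPAS after the headset comes off, to its planned end when the dressing is applied, and analyse it under the assigned condition. Use a partial score only if observation had to end, and flag it. Do not substitute Holding for the port-access score: it would miss distress arising at access and understate that visit's anxiety, in the same direction as dropping it.
- **Second visit:** offer the non-VR visit to a child stopped at a first VR visit. This involves no further VR exposure.
- **7.3 and 7.4:** include all observed scores in the mixed model and in the Z statistic. Report stops by condition at the interim and final analyses.

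The cost is a short amendment to the three removal passages and a line each in 7.3 and 7.4, with no visits beyond the two planned. The downside is that some scores will reflect a session in which VR was stopped early, and a few observations will be partial.

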5.0 SAFETY MONITORING

5.1 Definition of an Adverse Event

Any issues experienced while being observed by the research team should be recorded as a potential adverse event for evaluation by the PI as to the seriousness, relatedness, and expectedness in relation to the study.

It is expected that a patient may experience some discomfort or motion sickness while using VR.

5.2 Data and Safety Monitoring Plan

The researchers will be monitoring should a patient encounter any issues, particularly any discomfort or motion sickness while using the VR device. If so, the VR device will be removed, and the subject will be eliminated from the study.

The study staff will record all concerns experienced by enrolled subjects, the total number of side effects experienced by all enrolled subjects, and the number of subjects eliminated from the study due to side effects.

Reporting requirement: The principal investigator will oversee the subject safety and data records and report all pertinent information to the IRB, as necessary.

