Title	Randomized Pilot Crossover Study Comparing Virtual Reality (VR) and Non-VR Distraction for Decreasing Preoperative/Procedural Anxiety as a Function of the modified Yale Preoperative Anxiety Scale (mYPAS)
Short Title	VR-mYPAS study
Protocol Number	STU-2020-0607
Phase	Pilot
Methodology	Cross Over Design
Study Duration	Up to two years
Study Center(s)	Single-center – Children's medical center, Dallas, Texas
Objectives	To use the modified Yale Preoperative Anxiety Scale (mYPAS) to evaluate children prior to and during Port access, to look for a decrease preoperative anxiety during distraction in pediatric oncology patients undergoing port access.
Number of Subjects	77 patients
Diagnosis and Main Inclusion Criteria	CCBD patients requiring port access twice within a year
Study Product(s), Dose, Route, Regimen	mYPAS scoring while playing VR device versus non-VR distraction for Port access
Duration of administration	~ 15 minutes maximum (observation and completion of questionnaires after 10-minute familiarization with distraction method, during port access)
Reference therapy	N/A
Statistical Methodology	Cross over study will be performed. Subjects will be randomized (1 to 1 randomization via Proc Plan in SAS 9.4) at their initial encounter to either VR or Non-VR. During their second visit patients will be given the alternative mode of care (i.e. patients who initially received VR distraction will be given Non-VR distraction, and patients who initially received Non-VR distraction will receive VR distraction)

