6.0 TREATMENT INFORMATION

6.1 Potential Risks of VR distraction

While this study is considered low risk, patient discomfort and motion sickness are potential risks. Should a patient experience any discomfort or motion

sickness, VR device will be removed, and the subject will be excluded from study. Disposable VR covers will be used, and device will be sanitized between patients to minimize risk of infection.

There is a risk of the loss of confidentiality, but measures will be taken to minimize this risk, such as only the named study staff will be handling the study forms and all the subjects will be assigned unique study numbers. The only document that could identify a patient is the informed consent that would be linked to a study participant by a study number. These informed consents will be kept in a locked cabinet in the locked office of the principal investigator. No other identifiers will be collected as a part of the research data that links a study number to the patient PHI.

For the safety of the researchers and patients, all mYPAS patient observations on day of CCBD visit, as well as any further consent questions, will be performed through a virtual telemedicine platform with approved tablets run and vetted by telemedicine at Children's Health System of Texas (CHST). The process has already been approved and vetted by CHST telemedicine so that there is little to no risk of virtual PHI breach.

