7.3 Data Analyses

Categorical outcomes will be presented as frequency and percentages and compared using chi-square and/or Fisher's exact test. Continuous outcomes will be summarized by median and inter-quartile range (IQR) OR mean and standard deviation (depending on the data's distribution). Depending on the data's distribution a paired t-test or Wilcoxon-sign rank test will be performed to assess the difference between VR distraction and Non-VR distraction. For this crossover design a mixed model will also be implemented, which accounts for

treatment/intervention (VR vs. non-VR), sequence, and period as fixed effects. Patients will be nested within sequence.

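### Children who do not tolerate VR are removed after randomisation, and the plan does not keep their recorded mYPAS scores in the VR versus non-VR comparison

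*Combined protocol and SAP*

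**What the plan says.** All sections are in the combined protocol and SAP.

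- **5.2:** if a child has discomfort or motion sickness while using the device, "If so, the VR device will be removed, and the subject will be eliminated from the study". Staff must record concerns, side effects and the number removed for side effects.
- **6.1** repeats the rule: "VR device will be removed, and the subject will be excluded from study".
- **5.1** anticipates the trigger: "It is expected that a patient may experience some discomfort or motion sickness while using VR".
- **4.4** separately allows removal at the child's request or for distress.
- **7.3:** "a paired t-test or Wilcoxon-sign rank test will be performed to assess the difference between VR distraction and Non-VR distraction". It then adds: "For this crossover design a mixed model will also be implemented", with treatment, sequence and period as fixed effects. It names no analysis set and no missing-data rule.
- **7.2** allows for 10% attrition and treats any excess as a matter of power.
- **7.4** sets a two-sided boundary, with one side for exacerbated anxiety, and does not say which children enter the tests.
- **4.2** has two mYPAS observations in the VR visit: Holding, in the first minutes with the headset on, and port access, from opening the kit. A removed child may therefore have a Holding score, a port-access score, both or neither.
- **8.4** transfers form data to REDCap after enrolment and then discards the paper forms. It does not mention removed children.

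**The concern.** The removal is a post-randomisation event whose named cause arises in only one of the two conditions. What happens to the data depends on sequence. A VR-first child removed at the first visit never has a non-VR score, so a paired test drops that child even if the VR score is kept. A non-VR-first child removed at the second visit stays in a paired test only if a VR score was recorded and kept.

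If the children lost are those whose VR score is high relative to their own non-VR score, the remaining pairs make VR look better than it is. A result in children who tolerated VR could then be read as the effect of offering VR. These are also the children in whom an anxiety-raising effect might show, so the 7.4 harm boundary would lose sensitivity. Read literally, 8.4 also makes an omitted score hard to recover, because the paper forms are discarded (8.7 on record retention reads differently).

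**Working it through.** **Plan's own figure.** Inputs from 7.2 and 7.4: difference 3.5, SD 10, two-sided alpha 0.05, power 0.80, attrition 10%. Reading SD 10 as the SD of the within-child difference:

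- Normal approximation: (10 × (1.960 + 0.842) / 3.5)² = 64.07, so 65 pairs.
- Paired t-test: 67 pairs (power 0.806); 67 / 0.9 = 74.4, so 75.
- Wilcoxon allowance (relative efficiency 0.955): 67 / 0.955 = 70.2; × 1.1 = 77.2, or / 0.9 = 78.0.

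The planned 77 is reproduced closely enough and is not in dispute.

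**Assumptions, none given in the documents.** SD 10 per visit and between-visit correlation ρ = 0.5, so the SD of the difference is √(100 + 100 − 2 × 0.5 × 100) = 10. A child is removed when a latent discomfort variable, with correlation c to the VR score, exceeds a cut-off z that removes a fraction p. For 77 children, p = 2%, 5% or 10% is 1.5, 3.9 or 7.7, about 2, 4 or 8 children.

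**Paired test, all removed children dropped.** Shift = −(1 − ρ) × 10 × c × φ(z) / (1 − p). With c = 0.5 the multiplier is 0.5 × 10 × 0.5 = 2.5:

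- p = 2%: −2.5 × 0.0484 / 0.98 = −0.12
- p = 5%: −2.5 × 0.1031 / 0.95 = −0.27
- p = 10%: −2.5 × 0.1755 / 0.90 = −0.49

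Dividing the shift by p gives the excess VR-minus-non-VR difference that c = 0.5 implies in removed children relative to the rest: 6.2, 5.4 and 4.9 points.

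Simulated error rates (100,000 trials per setting, fixed-sample two-sided 0.05):

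| Removed | Shift | Share of 3.5 | False benefit (nominal 2.5%) | Power for a +3.5 harm | Same, sample loss only |
|---|---|---|---|---|---|
| 2% | −0.12 | 3% | 3.2% | – | – |
| 5% | −0.27 | 8% | 4.2% | 0.78 | 0.84 |
| 10% | −0.49 | 14% | 5.9% | 0.70 | 0.82 |

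With no removal, harm power at 77 pairs is 0.86.

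**Paired test, only VR-first removed children dropped (39 of 77).** Shift = −2.5 × φ(z) × (39/77) / (1 − p × 39/77) = −0.06, −0.13 and −0.23. False benefit is about 2.8%, 3.2% and 3.9%; harm power at 5% and 10% is 0.82 and 0.79.

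**Interim harm boundary (Z ≥ 2.431, 52 children enrolled).** With a true +3.5 harm and no removal, the chance of crossing is 0.51. At 5% and 10% removal with c = 0.5 it is 0.41 and 0.34, against 0.48 and 0.46 from sample loss alone. These figures convert t to Z. Comparing t directly with 2.431 gives 0.45 and 0.37, against 0.51 and 0.49.

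**Sensitivity (paired, all dropped).**

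- c = 0.2 at 5% and 10%: −0.11 and −0.20. c = 0: no shift. c = −0.2: +0.11 and +0.20.
- ρ = 0.3 or 0.7 at 5%, c = 0.5: −0.38 or −0.16.
- If 2% are also removed under non-VR (4.4), tied equally to that score, the 5% shift falls to −0.15. With equal rates it is zero.

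**Mixed model (treatment, sequence, period; c = 0.5; 40,000 trials).**

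| VR scores of removed children | Shift at 5% / 10% | False benefit |
|---|---|---|
| Not kept | −0.33 / −0.61 | 4.6% / 7.1% |
| Kept | 0.00 / 0.00 | 2.6% / 2.5% |
| Kept, but half were never taken at that time point | −0.16 / −0.29 | 3.3% / 4.3% |

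Harm power with scores kept is 0.86 and 0.85. The zero shift holds because, in this simulation, removal depends on the non-VR score only through the observed VR score.

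**The case against.** The strongest reply is that the defect is inferred from silence. In a safety section, elimination naturally means the end of participation, not deletion of data, and 8.4 sends form data to REDCap with no exception for removed children. The mixed model in 7.3 can use one-visit data and, with scores kept, shows no bias. This narrows the problem but does not remove it. No section defines who is analysed, the mixed model is listed in addition to the paired test, and the paired test loses the VR-first children whatever is stored.

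The direction is also unproven. The trigger is discomfort or motion sickness, while mYPAS scores anxiety, and no section links the two. The correlation of 0.5 has no source. At 0.2 the shift is 3% or 6% of the target (0.11 / 3.5 and 0.20 / 3.5), with false benefit about 3.1% and 3.5% at 5% and 10% removal. Section 1.2 calls side effects minimal, and 10% removal would use the whole attrition allowance. All this stands: at 2% removal the effect is small.

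Finally, intolerance itself is not hidden, because 5.1, 5.2 and 8.4 have it recorded and adverse events reviewed. That is correct. What can be weakened is the mYPAS comparison and its harm boundary.

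**Conclusion.** The concern holds and should be fixed, with medium confidence. Following the plan as written can drop randomised children for a reason specific to VR, and nothing in it guarantees that their scores count. The size is conditional on an unstated removal rate and an unstated link to the VR score. At c = 0.5 and 2% to 10% removal, the completers-only shift is 0.12 to 0.49 points towards VR, false benefit is 3.2% to 5.9% against 2.5%, and harm power at 10% falls to 0.70 where sample loss alone would give 0.82. If removal is unrelated to the VR score only numbers are lost; if it is negatively related the bias runs against VR. Keeping the scores and using the mixed model removes the shift where a VR score exists at the time point compared.

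**What to change.** The clinical removal rules in 4.4, 5.2 and 6.1 are not at issue; the change concerns data only.

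1. **5.2 and 6.1:** state that stopping VR or leaving the study ends participation but does not remove mYPAS scores already recorded, and that these go to REDCap with the rest (8.4).
2. **7.3:** make the planned mixed model the basis of the VR versus non-VR comparison, in all randomised children with at least one mYPAS score, analysed as randomised. Compare Holding with Holding and port access with port access, so that a child removed before port access contributes only a Holding score. The Study Summary intends "to evaluate children prior to and during Port access", but the non-VR paragraph of 4.2 mentions scoring only before access; confirm that both scores are taken in both conditions.
3. **7.4:** use the same dataset at the interim and final tests.
4. **Reporting:** give removals and missing port-access scores by sequence and period.
5. **Optional:** a sensitivity analysis giving removed children an unfavourable VR score, mainly for port access, where retention cannot supply a score never taken.

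The cost is a wording amendment, with no added visits. The downsides are that a few VR scores from partial exposure enter the analysis, the estimate may be slightly less favourable to VR, and the port-access comparison is only partly protected.
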